## 10.3 Statistical Analyses

The statistical analysis plan will be developed and finalized before database lock and will describe the selection of participants to be included in the analyses, and procedures for accounting for missing, unused, and spurious data. Below is a summary of planned statistical analyses of the primary and secondary endpoints.

A description of the participant population will be included in a statistical output report, including subgroups of age, gender, and race.

### 10.3.1 Efficacy Analyses

Endpoint	Statistical Analysis Methods
Primary	DCR is defined as the proportion of participants who achieve a confirmed best response of CR, PR, or SD for at least 6 months after first treatment dose using the RECIST 1.1. The number and percentage of participants in each category of BOR (CR, PR, SD, PD, or UTD) as per RECIST 1.1 criteria will be presented. An estimate of the response rate and an associated exact 2-sided 95% CI (Clopper and Pearson) will be presented.
Secondary	OS is defined as the time from first dose date to the date of death from any cause. For participants that are alive, their survival time will be censored at the date of last contact ("last known alive date"). OS will be censored for participants at the date of first dose if they were treated but had no follow-up. A similar analysis as in PFS will be conducted for OS.
	ORR is defined as the proportion of participants who achieve a best response of CR or PR using the RECIST1.1 criteria.
	DOR is defined as the time between the date of first documented confirmed response (CR or PR) to the date of the first documented progression as per RECIST 1.1 or death due to any cause, whichever occurs first. For participants who neither progress nor die, the DOR will be

Endpoint	Statistical Analysis Methods
	
censored at the same time they will be censored for the primary definition of PFS. DOR will be evaluated for responders (ie, participants with confirmed CR or PR) only.

	
The primary definition of PFS is specified as the time between the date of first dose and the first date of documented progression as per RECIST 1.1 criteria or death due to any cause, whichever occurs first. Participants who die without a reported progression will be considered to have progressed on the date of their death. The following censoring rules will be applied for the primary definition of PFS.
 

• Participants who did not progress or die will be censored on the date of their last evaluable tumor assessment.

• Participants who did not have any on-study tumor assessments and did not die will be censored on their date of first dose.

• Participants who receive subsequent systemic anticancer therapy prior to documented progression will be censored at the date of the last tumor assessment prior to the initiation of the new therapy.

 
Median PFS will be estimated via the Kaplan-Meier product limit method. Two-sided 95% CI for the median PFS will be computed. Kaplan-Meier plots of PFS will be presented. The totality of PFS results will be presented in a single graphical display that includes the Kaplan-Meier curve and the median estimate and corresponding CIs.
 
The secondary definition of PFS is defined as the time between the date of first dose and the first date of documented progression as per RECIST 1.1 criteria or death due to any cause, whichever occurs first. Participants who die without a reported progression will be considered to have progressed on the date of their death. The following censoring rules will be applied for the secondary definition of PFS.
 

• Participants who did not progress or die will be censored on the date of their last evaluable tumor assessment.

• Participants who did not have any on-study tumor assessments and did not die will be censored on their date of first dose.

 
PFS based on investigator assessments will also be analyzed applying both the primary and the secondary definitions.
 
More detail on PFS will be provided in a separate Statistical Analysis Plan.

	
TTR is defined as the time from first dose date to the date of the first confirmed documented response (CR or PR) per RECIST 1.1 criteria. TTR will be evaluated for responders among the population of interest (ie, participants with a BOR of CR or PR).

Abbreviations: BOR = best overall response; CI = confidence interval; CR = complete response; DOR = duration of response; OS = overall survival; PFS = progression-free survival; PR = partial response; RECIST 1.1 = Response Evaluation Criteria In Solid Tumors version 1.1; SD = stable disease; TTR = time to objective response; UTD = unable to determine

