## **10 STATISTICAL CONSIDERATIONS**

### **10.1 Sample Size Determination**

The sample size of the study is based on a Simon 2-stage design that will test whether retreatment with ipilimumab in combination with nivolumab in patients with mRCC progressing on maintenance nivolumab after first-line therapy with ipilimumab and nivolumab yields a DCR that is of clinical interest.

In this study, a DCR in excess of 20% will be considered of clinical interest. The Simon design will test the null hypothesis that the true DCR is less than or equal to 20% versus the alternative hypothesis that it exceeds 20%. The type I error rate will be 5% for a 1-sided test and the design will have 85% power to reject the null hypothesis when the true DCR is 35%.

The Simon design in this study requires 27 response-evaluable patients for the first stage. The patients included in the first stage analysis will be followed for at least 2 scans approximately 4 months after first dose. The enrollment will not be stopped during the first stage analysis so this relatively shorter follow-up period will be used in order to mitigate risk to patients being enrolled but not included in the first stage analysis. This analysis will quantify patients without progression. For example, confirmed responders, patients with unconfirmed response without progression, and patients with SD on consecutive scans would all qualify as having disease control. If there are exactly 27 patients in the first stage, then 7 or more of these patients, or at least 26%, will warrant proceeding to the second stage. Otherwise, enrollment will be stopped.

The enrollment will stop when either futility is declared at Stage 1 or once approximately 80 response-evaluable participants have been treated. Approximately 96 participants will be enrolled in order to obtain 80 response-evaluable patients, accounting for approximately 20% of

non-evaluable patients or withdrawal. The number of enrolled participants with SD  $\geq$  6 months will be capped at 50%.

The duration of the trial is expected to be approximately 24 months of treatment (Stage 1 + Stage 2) and 36 months of follow-up after the last participant first dosing. A futility analysis will be performed after Stage 1 and the primary analysis will be conducted upon completion of Stage 2.

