## 10.2 Populations for Analyses

For purposes of analysis, the following populations are defined:

Population	Description
Enrolled	All participants who sign informed consent and were registered into the IRT
Response Evaluable	All participants with baseline and at least 1 on-study tumor assessment who received at least 1 dose of study treatment. Analysis of demography, protocol deviations, baseline characteristics, and efficacy will be performed on this population.
Safety	All participants who take at least 1 dose of study treatment. This is the primary dataset for drug exposure and safety analysis.

Abbreviation: IRT = interactive response technology.

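### Section 10.1 promises a one-sided 5% test of DCR, but Section 10.3.1 states neither a test nor a final rejection count, and the right count depends on which endpoint gates Stage 1

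*Combined protocol and SAP*

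**What the plan says.** Section 10.1 commits to a hypothesis test: "The Simon design will test the null hypothesis that the true DCR is less than or equal to 20% versus the alternative hypothesis" that it is higher. It adds that "The type I error rate will be 5% for a 1-sided test and the design will have 85% power" at a true DCR of 35%. Sections 10.1 and 10.3.5 give the stage sizes (27, then 53 more) and one decision count: continue if at least 7 of the first 27 have disease control.

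That Stage 1 count is not the primary endpoint. Section 10.1 follows Stage 1 patients for two scans, about 4 months, and counts those without progression, including unconfirmed responses. The primary DCR requires a confirmed CR or PR, or SD lasting at least 6 months.

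For the primary endpoint, Section 10.3.1 lists the best-response categories and then states: "An estimate of the response rate and an associated exact 2-sided 95% CI (Clopper and Pearson) will be presented". It gives no test, p-value, rejection count or comparison with 20%.

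The final number is approximate. Enrollment ends "once approximately 80 response-evaluable participants have been treated", and Section 10.2 defines evaluable as "All participants with baseline and at least 1 on-study tumor assessment who received at least 1 dose of study treatment".

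**The concern.** The analysis section does not carry out the test that justified the sample size, and the number of disease-control patients that makes the trial positive is not written down. Three things follow.

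- The only inferential output named for the primary endpoint is a two-sided 95% interval. It corresponds to one-sided 2.5%, not 5%, and takes no account of the futility stage.
- The interval is attached to a response rate, although the endpoint is DCR and ORR has its own row in the same table.
- The count that can be recovered from Section 10.1 assumes one endpoint at both stages, and the protocol uses two.

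At stake is whether the reported conclusion has the 5% and 85% that the protocol states, and whether the cut-off is fixed before an open-label trial's results are known.

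**Working it through.** **Inputs.** Null 20%, alternative 35%, one-sided 5% and 85% power (Section 10.1); 27 + 53 = 80 and continue at 7 or more of 27 (Sections 10.1 and 10.3.5); two-sided 95% Clopper-Pearson interval (Section 10.3.1).

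**Step 1: reproduce the design, with the same endpoint at both stages.** For a final cut-off r and true rate p,

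P(reject) = Σ from x = 7 to 27 of P(X1 = x) × P(X2 ≥ r − x), with X1 ~ Bin(27, p) and X2 ~ Bin(53, p).

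| Cut-off of 80 | Two-stage type I error (p = 20%) | Power (p = 35%) | One-stage tail, P(Bin(80, 0.20) ≥ r) | 95% CP lower limit | 90% CP lower limit |
|---|---|---|---|---|---|
| 21 | 7.45% | 86.8% | 10.7% | 17.0% | 18.3% |
| 22 | 4.94% | 85.3% | 6.6% | 18.1% | 19.4% |
| 23 | 3.08% | 82.9% | 3.9% | 19.2% | 20.5% |
| 24 | 1.81% | 79.3% | 2.2% | 20.3% | 21.6% |

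Only 22 meets both stated targets. A grid search also returns 27/80 with cut-off 22 as the Simon optimal design for these inputs, so the sample size in Section 10.1 reproduces.

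**Step 2: compare with the planned interval.** The 95% lower limit first exceeds 20% at 24 of 80. If the interval were read as a test, type I error would be 1.8% and power 79.3%. It would differ from the design rule at 22 and 23 of 80. The chance of landing there after passing Stage 1 is 4.94% − 1.81% = 3.1% at DCR 20%, about 13% at 30%, and 85.3% − 79.3% = 6% at 35%. An ordinary 90% interval still misses at 22 (19.4%). A one-sided 95% bound from inverting the two-stage tail probability agrees with the test there (20.03%).

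**Step 3: use the Stage 1 gate that the protocol describes.** Let q be the probability of passing the 4-month criterion, and assume that every patient with eventual DCR passes it. Then G ~ Bin(27, q) must be at least 7, and of those G patients Bin(G, p/q) reach DCR. The documents give no q, so it is assumed.

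- At p = 20%, 22 or more of 80 gives 6.3% with q = 30% and 6.6% with q = 45%. The ceiling is the one-stage tail, 6.6%.
- At p = 20%, 23 or more of 80 cannot exceed its one-stage tail, 3.9%, whatever the gate.
- At p = 35% with q = 45%, power is 93.0% for 22, about 90% for 23 and 84.9% for 24.

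**Step 4: let the final n differ from 80.** If 20% of the 96 enrolled were non-evaluable, 96 × 0.80 = 76.8 would remain; with no loss, 96. Under the Step 1 formula, with n − 27 patients in Stage 2, the smallest cut-off holding 5% is 22 for n = 76–80, 23 for 81–84, 24 for 85–89, 25 for 90–93 and 26 for 94–96. Keeping 22 regardless would give 3.2% at 76, 5.4% at 81 and 7.1% at 84. At n = 76 the power is 82.1%, below the stated 85%.

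**The case against.** A reader might infer that the protocol contains two conflicting decision rules, so that 22 or 23 of 80 would be positive by design and negative by the planned analysis. The documents do not support that. Section 10.3.1 says only that the interval is to be presented; nothing compares it with 20% or makes it the success criterion. A one-sided 5% test reported beside a descriptive two-sided 95% interval is ordinary practice. The primary objective is itself worded as descriptive, and the 24-of-80 rule exists only if a reader imposes it.

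It can also be said that Section 10.3 is a summary, that a separate SAP is promised, that the design schematics are not shown and could carry the count, and that the stated inputs already determine 22.

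Most of this stands, and it limits the point to an omission. It does not remove the point. Section 10.3 requires the SAP only before database lock, and what it and Section 10.3.5 defer (participant selection, missing data, interim analyses) does not expressly include the final rejection rule. The inputs determine 22 only if Stage 1 and the final analysis count the same endpoint, which Section 10.1 contradicts. The response-rate wording sits in the DCR row and needs only an editorial correction.

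**Conclusion.** The point holds as an omission with a numerical consequence. The primary analysis as written does not carry out the test in Section 10.1, and no readable text gives the final count. The count implied by Section 10.1 is 22 of 80 (4.94%, 85.3%), valid only with one endpoint at both stages. With the 4-month gate that Section 10.1 describes, the same count gives about 6.3% to 6.6% under the null, so simply writing in 22 would not deliver 5%.

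The 4-month range rests on assumed rates of 30% to 45% and on DCR patients all passing the gate; the figures for 80 assume exactly 80 evaluable patients. The excess over 5% is modest, and the outcomes on which the interval and the design count would differ are few. Severity: should-fix.

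**What to change.** In Sections 10.1 and 10.3.1, name DCR as the quantity estimated and tested, and state the final rule together with the Stage 1 endpoint. Either option works.

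- **(a) Stage 1 gated on the same DCR endpoint.** Reject at 22 or more of 80. Report a two-stage p-value and a two-sided 90% interval based on the two-stage sample space. The stated 5% and 85% then stand. Stage 1 would have to wait for the 6-month status, which gives up the shorter follow-up that Section 10.1 chose deliberately while enrollment continues.
- **(b) 4-month gate kept.** Reject at 23 or more of 80. Report a two-sided 90% Clopper-Pearson interval, whose lower limit exceeds 20% exactly from 23 of 80 (20.5%). Type I error is at most about 4%. Restate the power at DCR 35%: 82.9% with a same-endpoint gate, about 90% if the 4-month rate is 45% (assumed).

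Under either option, prespecify that the count is recomputed for the actual evaluable n. For (a), use the counts in Step 4 of the working. For (b), use the smallest r with P(Bin(n, 0.20) ≥ r) ≤ 5%. Label the 95% interval descriptive. If the sponsor would rather have the 95% interval decide, state that and restate the same-endpoint figures as 1.8% and 79.3%.

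The cost is protocol and SAP wording and a short program, plus the later Stage 1 look under (a). The planned sample size is unchanged and no new data are collected.

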## 4 OBJECTIVES AND ENDPOINTS

**Table 4-1: Objectives and Endpoints**

Objectives	Endpoints
Primary	

To describe the efficacy in terms of DCR of retreatment with ipilimumab in combination with nivolumab in patients with mRCC progressing on maintenance nivolumab after first-line therapy with ipilimumab and nivolumab

	

DCR is defined as the proportion of participants who achieve a confirmed best response of CR, PR, or SD for at least 6 months after first treatment dose per RECIST 1.1 criteria.

Secondary	

To describe the OS of retreatment with ipilimumab in combination with nivolumab in patients with mRCC progressing on maintenance nivolumab after first-line therapy with ipilimumab and nivolumab.

To evaluate additional efficacy measures in all participants.

	

OS is defined as the time from first dose to the date of death from any cause. For participants that are alive, their survival time will be censored at the date of last contact (“last known alive date”). OS will be censored for participants at the date of first dose if they were treated but had no follow-up.

ORR is defined as the proportion of participants who achieve a best response of CR or PR per RECIST 1.1 criteria.

DoR is defined as the time between the date of first documented response (CR or PR) to the date of the first documented progression, per RECIST 1.1 criteria, or death due to any cause, whichever occurs first.

PFS is defined as the time between the date of first dose and the first date of documented progression, as per RECIST 1.1 criteria, or death due to any cause, whichever occurs first.

Time to objective response (TTR) is defined as the time between the date of the first dose and the first confirmed documented response (CR or PR) per RECIST 1.1 criteria.

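### As written, DOR runs to death for a responder who starts new systemic therapy without documented progression, although primary PFS for that participant is censored before the therapy

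*Combined protocol and SAP*

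**What the plan says.** All the rules are in Section 10.3.1 (Efficacy Analyses) unless another place is named.

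- **DOR event.** DOR runs from response "to the date of the first documented progression as per RECIST 1.1 or death due to any cause, whichever occurs first". Death after a new therapy is not excepted.
- **DOR censoring.** "For participants who neither progress nor die, the DOR will be" "censored at the same time they will be censored for the primary definition of PFS". No other DOR censoring rule is given.
- **Primary PFS, new therapy.** "Participants who receive subsequent systemic anticancer therapy prior to documented progression will be censored at the date of the last tumor assessment" that precedes the new therapy. Later death is not mentioned. This bullet is the only difference between the primary and secondary PFS definitions.
- **Both PFS definitions, death.** "Participants who die without a reported progression will be considered to have progressed on the date of their death". The text does not say whether this sentence or the new-therapy bullet governs when both apply.
- **Follow-up.** Section 5.1 ends tumor assessments when another anti-cancer treatment starts. It continues survival follow-up every 3 months for about 36 months.
- **DOR start date.** Table 4-1, like the synopsis, has "DoR is defined as the time between the date of first documented response (CR or PR"). Section 10.3.1 has "DOR is defined as the time between the date of first documented confirmed response (CR or PR").

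**The concern.** The plan means DOR to share its censoring with primary PFS, but the sharing clause leaves out participants who die. Scans stop at new therapy, so later progression will usually go undocumented, while deaths will still be recorded. Take two responders with the same scans who start the same new therapy on the same day. The one who stays alive is censored at the last scan before it. The one who dies is counted as responding until death.

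Two things follow. Whether a participant is censored before the new therapy is decided by what happens after it, so the censoring is informative. And part of the DOR credited to retreatment may have been spent on a different treatment. In the published tables, a participant's DOR and PFS could then conflict.

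**Working it through.** The plan states no figure to reproduce. The check applies the written rules to single responders and then looks at the likely size.

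**Inputs.** Scans at Week 12, every 8 weeks to Week 60, then every 12 weeks (Table 2-3). The event and censoring rules are from Section 10.3.1. The dates of response, new therapy and death are assumed.

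**Formulas.** Let R be the response week, C the last scan before new therapy and D the week of death, with no documented progression.

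- Primary PFS = C, censored
- DOR as written = D − R, event
- DOR under the primary PFS rule = C − R, censored
- DOR as written exceeds PFS when D − R > C, that is, when D > C + R

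| R | New therapy | C | D | Primary PFS | DOR as written | DOR under PFS rule | C + R | DOR > PFS? |
|---|---|---|---|---|---|---|---|---|
| 12 | 30 | 28 | 100 | 28, censored | 88, event | 16, censored | 40 | yes |
| 12 | 30 | 28 | alive | 28, censored | 16, censored | 16, censored | – | no |
| 12 | 38 | 36 | 45 | 36, censored | 33, event | 24, censored | 48 | no |
| 12 | 38 | 36 | 60 | 36, censored | 48, event | 24, censored | 48 | yes |
| 12 | 38 | 36 | 104 | 36, censored | 92, event | 24, censored | 48 | yes |
| 20 | 50 | 44 | 60 | 44, censored | 40, event | 24, censored | 64 | no |

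Rows 1 and 2 differ only in vital status after the new therapy, yet DOR goes from 16 weeks censored to an 88-week event. Under the primary PFS rule DOR is always C − R, which cannot exceed C.

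**How many participants.** If ORR were 23%, the figure Section 3.2.5 gives for the retrospective salvage study, 80 response-evaluable participants would yield 0.23 × 80 = 18.4, about 18 responders. The documents do not say how many would start new therapy before progression. Shares of 10% to 30% were assumed.

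**Effect on the median.** In a simulation of 20,000 responders (assumed medians: 52 weeks to progression, 78 weeks from new therapy to death; 36 months of follow-up), the Kaplan-Meier median DOR was:

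| Share starting new therapy first | PFS rule, weeks | As written, weeks |
|---|---|---|
| 10% | 51.4 | 51.4 |
| 20% | 51.2 | 51.2 |
| 30% | 51.2 | 51.4 |

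Simulated trials of 18 responders vary more. With 2 or 4 of them starting new therapy first, and an assumed median DOR of 30 or 52 weeks, the typical change was zero. The median moved in 23% to 59% of trials, and the mean change was 0.2 to 4.7 weeks shorter as written. With a 52-week median and 10% to 30% starting new therapy, the shift was at least 8 weeks in 9% to 23% of trials. The direction is not fixed by the rule: deaths that would have been censored become events, which tends to shorten the median, while late deaths keep a participant at risk for longer. With shorter durations and more new therapy, the mean change lies near zero and can take either sign.

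**Start date.** A response first seen at Week 12 and confirmed at Week 20 gives start dates 20 − 12 = 8 weeks apart, if the 10.3.1 wording is read as the date of confirmation.

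**The case against.** The best counter-argument is that primary PFS may itself run to death. The sentence "Participants who die without a reported progression will be considered to have progressed on the date of their death" carries no exception, and nothing ranks it below the new-therapy bullet. If it governs, PFS is also an event at death and the two endpoints agree. But the bullet would then have no effect for anyone who dies, and the primary and secondary definitions would be nearly the same. The dependence on later vital status would also remain, now in both endpoints. Reading the specific bullet as controlling is the better construction. What stands is that the PFS text is ambiguous too, so correcting DOR alone would not be enough.

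Second, the intent to align is visible, since DOR names the primary PFS definition, and Section 10.3 calls itself a summary to be completed by an SAP before database lock. That makes this a drafting defect rather than a deliberate analysis choice. It does not remove it: the deferral within 10.3.1 names PFS, not DOR, and an SAP that repeated the sentence would repeat the gap.

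Third, the start-date wording can naturally be read as the first documented response in a participant whose response is later confirmed, which fits Table 4-1 and the synopsis. That stands. It is a wording alignment only.

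**Conclusion.** The mismatch is real on the current text. It requires subsequent systemic anticancer therapy before documented progression, followed by death, and it rests on the new-therapy bullet controlling primary PFS. If progression is documented before the new therapy, the two endpoints share the same event.

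A reader might infer three stronger things that the documents do not support:

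- **DOR will exceed PFS.** It does so only when D > C + R, and the comparison sets an event time against a censored time.
- **A few such participants would lengthen the median.** The simulations show little average change, more often towards a shorter median. Single-trial shifts are possible in about 18 responders, but that count and the share starting new therapy are assumptions.
- **This weakens the main evidence for retreatment.** Section 3.1 measures regained control by DCR and lists OS, PFS, ORR and safety as key secondary endpoints; DOR is not among them. DOR is a descriptive secondary endpoint, and neither the DCR test nor the Stage 1 decision uses it.

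What remains is inconsistent, outcome-dependent handling of individual DOR values and the tail of the curve, with occasional unpredictable movement of the median. It is worth correcting before database lock, so that the choice is not made with the data in view.

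**What to change.** 1. In 10.3.1 and the SAP, state that DOR uses the same event and censoring dates as the primary definition of PFS for every responder, including censoring at the last tumor assessment before subsequent systemic therapy.
2. In the primary PFS definition, state that the new-therapy rule takes precedence over the death sentence when death follows new therapy.
3. As a minor alignment, use one DOR start date in the synopsis, Table 4-1 and 10.3.1: the first scan meeting CR or PR criteria that is later confirmed.

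The cost is one sentence for DOR, one for PFS and the alignment of the start-date wording. No new data are needed, since Section 5.1 already has new anti-tumor therapy recorded on the CRF. The statistical downside is slightly more censoring in DOR.
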